## IV. JUSTIFICATION OF THE STUDY DESIGN

---

### A. Evaluation of pre-clinic data (if applicable)

Currently no pre-clinical studies have been performed on the device under evaluation named as ORIGIN. The pre-clinical data regarding the VANGUARD system are the property of Biomet and are not collected for the purpose of this study.

### B. Evaluation of relevant clinical data (Registries, PMS, PMCFs)

As part of Symbios PMS, a prospective surveillance is established on the evaluated device. It includes the surveillance of all relevant scientific journals and regular electronic database (EMBASE, PubMed) review. A list of pertinent publications for this study is in the section XX. BIBLIOGRAPHY.

post-market surveillance also includes the current ongoing Symbios PMCF study CLIN-G-008: Evaluation of the performance and the safety of the ORIGIN® knee prosthesis and of the KNEE-PLAN® ORIGIN® instruments. (Study launched in 2018)

This study is related to 399 primary Total Knee Replacements, performed between 2018 and 2020. Indications are coherent with Instructions for Use. The mean follow-up is 1.0 year (max 1.6 year)

Preliminary results:

- Number of procedures                    399
- Gender                                        Females 52 % / Males 48 %
- Age     Mean 71.0 years
- Mean weight                                81.1 kg (33-177)
- Mean height                                168.7 cm (143-193)
- Mean Body Mass Index                28.4 (13-68)

Outcomes regarding performance:

- FJS score: compared to preoperative value, the Forgotten Joint Score is significantly improved at 3-6 months and at 1 year. According to the validated grading, the mean preoperative score (12.9/100) is poor and the mean score at 3-6 months (42/100) and at 1 year (60.5/100) is good
- Oxford Knee Score: compared to preoperative value, the Oxford Knee Score is significantly improved at 3-6 months and 1 year. According to the validated grading, the mean preoperative score (24.8/48) is poor and the mean score at 3-6 months (36.6/48) and at 1 year (41.2/48) is good
- ✓ Many of the patients are satisfied about their surgery (96% of satisfied or very satisfied)

At a mean follow-up of 1.0 year:

- ✓ The per-operative complication rate is 0.25%

[figure not shown]
SYMBIOS		 symbios  Clinical Investigation Plan	F029.03
Date	27.11.2019		Distribution Informatique pdf
Auteur	BGA		
Contrôle	EBO		
Libération	RAQ		

- ✓ The postoperative complication rate without revision is 3.25%
- ✓ The postoperative complication rate with revision is 0.25%

The ORIGIN® Knee system is also followed in the UK National Joint Registry. The last Post-Market Surveillance (PMS) report is related to 19 primary Total Knee Replacement, surgeries were performed from December 2018 to January 2020. Indications are coherent with Instructions for Use. The mean follow-up is 0.6 years (max 1.2 years). At a mean follow-up of 0.6 year, the revision rate is 5.3 %. Clinical data to date are analyzed at short-term follow-up and need to be monitored at medium and long-term. (up to 10 years)

### C. Description of clinical development stage

The clinical development stages are part of global Symbios Clinical Strategy for Symbios products, during overall product lifecycle. ORIGIN is a medical device system followed in PMCF studies and registries (UK & SWITZERLAND) as part of post-market surveillance to compile sufficient data for Clinical Evidence.

### D. Post-Market Surveillance

Participation in this clinical study will not result in any direct benefit to the patient. Trial subjects implanted with ORIGIN System receive the same medical treatment as if they were not participating in this post-market study. Participation contributes to expansion of the knowledge base with respect to the use of the ORIGIN system in a routine hospital setting. This observational study will be used as part

SYMBIOS		 symbios  Clinical Investigation Plan	F029.03
Date	27.11.2019		Distribution Informatique pdf
Auteur	BGA		
Contrôle	EBO		
Libération	RAQ		

of clinical evaluation and post-market surveillance of the evaluated device. Results will be used to support the update of the Clinical Evaluation Report (CER) and Post-Market Surveillance Report (PMS).

SYMBIOS		 symbios  Clinical Investigation Plan	F029.03
Date	27.11.2019		Distribution Informatique pdf
Auteur	BGA		
Contrôle	EBO		
Libération	RAQ		

## V. RISKS AND BENEFICES OF THE EVALUATED DEVICE

### A. Anticipated clinical benefits

Participation in this clinical study will not result in any direct benefit to the patient. Trial subjects implanted with ORIGIN/VANGUARD, both CE marked devices, receive the same medical treatment as if they were not participating in this post-market study. This is emphasized by the fact that randomized controlled studies and assessments of patient reported outcomes are missing in the current scientific knowledge. Therefore, the current study aims to narrow this knowledge gap and provide Level of evidence for TKA by comparing the two similar TKA Prostheses mentioned above and to evaluate their clinical performance and safety.

However, the expected benefits of the ORIGIN® implants is to reduce the knee pain, increase the knee mobility, provide a stable knee, increase the knee function, and increase the quality of life of patients.

The hypothesis raised for this study, regarding the scoring, is that patients will experience a marked improvement in the natural feel of the prosthesis during the first year after the surgery, and slightly significant improvement at the following interval of 2 years. The overall patient satisfaction is expected to be improved after 2 years follow-up whether they receive ORIGIN or VANGUARD

### B. Residual risks

ORIGIN® Knee Implants has no innovative aspects compared to standard posterior-stabilized Total Knee Prosthesis. All the possible adverse events potentially caused by the implantation of ORIGIN® Knee Implants are known in the state of the art. These are also listed in the Instruction for Use of the evaluated devices, as listed below.

Adverse events	Severity	Probability in CER	Probability	Reduced risk score	Unanticipated Intolerable Harms?	Risk control measures
Infection	8	0.2 %	2		 yes  no	NA
Aseptic loosening	6	0.2 %	4		 yes  no	NA
Pain	6	0.7 %	4		 yes  no	NA
Stiffness	6	2.2 %	6		 yes  no	Monitored through PMCF/PMS
Malalignment	4	0 %	2		 yes  no	NA
Instability	4	0 %	2		 yes  no	NA
Dislocation/Subluxation	6	0 %	2		 yes  no	NA
Periprosthetic fracture	8	0.2 %	4		 yes  no	Monitored through PMCF/PMS

SYMBIOS		 symbios  Clinical Investigation Plan	F029.03
Date	27.11.2019		Distribution Informatique pdf
Auteur	BGA		
Contrôle	EBO		
Libération	RAQ		

Wear	4	0 %	2		 yes  no	NA
Adverse Soft tissues/lysis	6	0 %	2		 yes  no	NA
Allergy	6	0 %	2		 yes  no	NA
Component dissociation	8	0 %	2		 yes  no	NA
Implant fracture	8	0 %	2		 yes  no	NA

Stiffness is a common early adverse event identified in subjects who underwent a surgical procedure with the ORIGIN System.

Infection is also an identified postoperative adverse event as occurring to subjects who underwent a surgical procedure with the ORIGIN System.

The residual risks are monitored through a post-market surveillance, vigilance and customer feedback.

### C. Risks associated with participation in the clinical investigation

There are possible risks and side effects connected to the ORIGIN & VANGUARD implants (as described in the IFU), but the risks are similar to those for an implant of the ORIGIN & VANGUARD without participation in this study. The risks are known and consistent with the state of the art.

Clinical data to date for ORIGIN system are analyzed at short-term follow-up and need to be monitored at medium and long-term (up to 10 years).

Risks and events will be continuously monitored, assessed and documented by the investigator. Instructions for Use is a reference for the list of anticipated adverse events which may be associated with the use of the ORIGIN & VANGUARD System.

### D. Risks-to-benefit rationale

Appropriate risk management activities have been performed for ORIGIN system resulting in a positive risk-to-benefit rationale as confirmed by CE mark. Risks and potential benefits are similar for subjects being implanted as part of this study protocol compared to subjects implanted while not participating in this study. Symbios risk management report applied to the ORIGIN Knee System, is part of the technical file compilation and maintenance, and post-production activities of the product's lifecycle.

SYMBIOS		 symbios  Clinical Investigation Plan	F029.03
Date	27.11.2019		Distribution Informatique pdf
Auteur	BGA		
Contrôle	EBO		
Libération	RAQ		

## VI. STUDY OBJECTIVES

---

### A. Study purpose

The study objective is to assess patient satisfaction prior and after the surgery and to document the clinical and device performance outcomes of the ORIGIN System used in routine hospital practice in a large patient cohort treatment of total knee arthroplasty.

#### a) *Performance claim*

All data related to the evaluated device are part of Symbios clinical evaluation. Therefore, the performance claim is validated by the clinical evaluation.

#### b) *Safety claim*

The safety claim for the ORIGIN System is validated by the clinical evaluation. The revision rate is consistent with the state of the art. With a confidence interval of 95%, the revision rate is not higher than 2% at 1 year.

Specific claims for clinical performance and effectiveness of the ORIGIN System, is based on the state-of-the-art and is described in the clinical evaluation for the evaluated product.

The basis for the selection of the study endpoints includes the following considerations:

- They are clinically relevant and address important safety and efficacy aspects of the ORIGIN System.
- They are objectively defined and measurable in most subjects.
- They are consistent with current recommendations for endpoints in TKA clinical studies.

### B. Clinical endpoints

#### a) *Primary endpoints*

- The hypothesis regarding the scoring is that patients receiving ORIGIN implants will experience a more natural feel of the prosthesis during the first year after the surgery compared to patients receiving VANGUARD implants (as measured with FJS)
- The primary endpoint of this study is:

SYMBIOS		 symbios  Clinical Investigation Plan	F029.03
Date	27.11.2019		Distribution Informatique pdf
Auteur	BGA		
Contrôle	EBO		
Libération	RAQ		

- To compare the ability of patients to forget their operated knee at 1 year after the surgery, measured by the Forgotten Joint Score 12 (FJS-12 Knee).
- To compare patient satisfaction regarding the surgery with a CE marked custom-made implant (ORIGIN®) versus off-the-shelf (VANGUARD PS) device. A short self-reported questionnaire will be used.

*b) Secondary endpoints will evaluate clinical performance and safety of ORIGIN System:*

- **Secondary endpoints:**

- Evaluate the success of the procedure
- Evaluate surgeon satisfaction regarding the use of implants and instruments
- Evaluate outcomes: complications & revision rate with the ORIGIN SYSTEM at the last (2y) follow-up visit
- To compare the PROMs between the two groups at 1y follow-up and 2y follow-up visits.
- Evaluate performance of the ORIGIN System vs VANGUARD PS at 2 years follow-up: clinical examination and scoring.
- To evaluate/compare the clinical, functional and quality of life outcomes using the following four scores:
  - Clinical examination
  - The Knee Injury and Osteoarthritis Outcome Score (KOOS)
  - The Oxford Knee Score (OKS)
  - The EQ-5D-5L Score
  - A self-administrated patient satisfaction questionnaire.
- To evaluate/compare the clinical, functional and quality of life outcomes with the following surgeon reported scores:
  - The Knee Society Score (KSS) (Objective Knee Indicators only)
  - Knee Society Radiographic Evaluation and Scoring System (KSRESS)
  - The Single Leg Stance Test (SLS)
  - The Timed Up & Go test (TUG)
- Radiological evaluation:
  - X-rays: AP, lateral, sunrise, long leg weight bearing film
  - Femoral patellar arthrosis: Iwano classification (stage 1 mild to 4 very severe),
  - KRESS Radiological assessment: Patellar tilt angle, patellar displacement, tibial slope, anatomical axis (angles  $\alpha - \beta$ ), mechanical axis, (HKA angle, F angle, T angle, HKS angle)
  - Evaluate the radiographic limb alignment, radiolucent lines and radiographic loosening (according to the “Modern Knee Society Radiographic Evaluation System and Methodology for Total Knee Arthroplasty” version 2015)

 The self-administered patient satisfaction scale for primary hip and knee arthroplasty. N. Mahomed, Rajiv Gandhi, Lawrence Daltroy, and J. N. Katz  
doi:10.1155/2011/591253

SYMBIOS		 symbios  Clinical Investigation Plan	F029.03
Date	27.11.2019		Distribution Informatique pdf
Auteur	BGA		
Contrôle	EBO		
Libération	RAQ		

Endpoints evaluation is based on a significant improvement between preoperative & last follow-up at two years.

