	
 
• Severe collateral ligaments deficiency (requiring a more constrained prosthesis)
 
• Major anatomical deformities
 
• Severe flexion contracture or severe recurvatum
 
• Revision of a partial or total knee prosthesis
 
• Non-extractible material (e.g. screws, plate, intramedullary nail, osteosynthesis material...) which can create a conflict with any component of the prosthesis
 
• Distal and/or posterior and/or anterior femoral bone loss which exceeds the femoral component thickness
 
• Proximal tibial bone loss which exceeds the tibial component thickness (tibial tray + tibial insert)
 
• Allergy of any implant material
 

Collected data:	
 
• Baseline data: Year of birth, gender, weight, height, BMI, indication, medical knee history (number of surgeries, description, patient outcome), radiological examination or CT scan
 
• Surgery procedure: side of implantation, implanted devices ORIGIN (instruments included) vs VANGUARD PS, surgery total duration time, perioperative complications and difficulties, Surgeon satisfaction regarding devices and instruments, Femoral and tibial sizing, patellar resurfacing.
 
• Postoperative Follow-up: (1y, 2y) follow-up visits: Physical examination, weight, height, BMI Rx examination, safety evaluation, scoring via a questionnaire: FJS score (at 1y and 2y FU visits), patient satisfaction, surgeon reported scores (Knee Society Radiographic Evaluation and Scoring System (KSRESS, the Knee Society Score (KSS) (Objective Knee Indicators only), the Single Leg Stance Test (SLS) , the Timed Up & Go test (TUG) )and patient reported scores: KOOS, OKS, FJS; EQ-5D-5L, a self-administrated patient satisfaction questionnaire and complications, revisions.
 
 
FJS and other reported scores (at the postoperative visits) will be collected per standard of care at the investigational site and will be compared at each follow-up among ARM 1 and 2.

Clinical Affairs Manager:	[name]
Clinical Monitor:	TRIUM (Clinical Monitor)
eCRF platform:	Bepatient

SYMBIOS		 symbios  Clinical Investigation Plan	F029.03
Date	27.11.2019		Distribution Informatique pdf
Auteur	BGA		
Contrôle	EBO		
Libération	RAQ		

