### C. Hypothesis

The hypothesis regarding the scoring is that patients receiving ORIGIN implants will experience a more natural feel of the prosthesis during the first year after the surgery compared to patients receiving VANGUARD implants (as measured with FJS), and slightly significant improvement at the following interval of 2 years. The overall patient satisfaction is expected to be improved after 2 years follow-up. It is also supposed that the overall patient satisfaction is expected to be 13.4 points higher with ORIGIN PS than with VANGUARD PS treatment. (Cf. Chapter Statistical Analysis. Section A. Sample size calculation)

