### e) *Statistical Methods and Analysis*

All analyses will be described in a Statistical Analysis Plan (SAP) which will be completed prior to analysis. No interim analysis is planned.

Any deviations from this section and/or the Statistical Analysis Plan will be described and justified in the Final Clinical Study Report, as appropriate.

No statistical techniques will be used to impute missing data for continuous or categorical outcomes. If a subject's data are missing for any reason, that subject will not be included in that portion of the analysis. The number of subjects included in each analysis will be reported so that the reader can assess the potential impact of missing data.

Additional (annual) reports providing only descriptive statistics will only be written upon request of the EC/IRB and/or Regulatory Authority, as applicable.

For statistical analysis, patient satisfaction results will be analyzed into the knee awareness as:

- Never
- Almost never
- Seldom
- Sometimes
- Mostly

The subjects that required further procedures or surgeries on their knee in the initial six months were excluded from this analysis. These patients were excluded from analysis because the outcome and satisfaction scores were likely to be highly influenced by the early additional procedure, and the study was not powered to evaluate the revision rates associated with two implants.

Statistical differences could be identified in:

- Baseline demographics between ORIGIN vs VANGUARD in patient satisfaction, including slightly differences in age, comorbidities and sex.
- Surgeon overall satisfaction regarding both implants ORIGIN and VANGUARD and possible surgical factors who could play a role in the patient outcome or on the performance of the implant?
- Demonstrate superiority of ORIGIN over VANGUARD: higher score by 13.4 points based on MCID evaluation of PROMs.
- If a modular stem is used it could impact radiological analysis: radiolucencies for instance and tibial loosening

SYMBIOS		 symbios  Clinical Investigation Plan	F029.03
Date	27.11.2019		Distribution Informatique pdf
Auteur	BGA		
Contrôle	EBO		
Libération	RAQ		

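### Section VI.B judges endpoints by improvement from preoperative to 2 years, which conflicts with the planned between-arm comparisons; the sentence, the primary success rule and the FJS scoring text need correcting

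*Combined protocol and SAP*

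**What the plan says.** **The sentence at issue.** The last line of Section VI.B, after the radiological items of the secondary list, reads: "Endpoints evaluation is based on a significant improvement between preoperative & last follow-up at two years". It names no arm and no endpoint.

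**Between-arm statements elsewhere.**
- Primary endpoint (Synopsis and VI.B a): "To compare the ability of patients to forget their operated knee at 1 year after the surgery", measured by the FJS-12.
- Secondary patient-reported outcomes (VI.B b): "To compare the PROMs between the two groups at 1y follow-up and 2y follow-up visits". The Synopsis, under collected data, says that scores "will be compared at each follow-up among ARM 1 and 2".
- Hypothesis (VI.C): "It is also supposed that the overall patient satisfaction is expected to be 13.4 points higher with ORIGIN PS than with VANGUARD PS treatment".
- X.a sizes a two-group comparison of means, with effect size 13.4/26.8 and at least 63 per group. X.e lists: "Demonstrate superiority of ORIGIN over VANGUARD: higher score by 13.4 points based on MCID evaluation of PROMs".
- VIII.F c) and d), for the 1-year and 2-year visits, expect better satisfaction for ORIGIN against VANGUARD.

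**Before-and-after statements.** VI.A: "The study objective is to assess patient satisfaction prior and after the surgery". V.A: "The overall patient satisfaction is expected to be improved after 2 years follow-up whether they receive ORIGIN or VANGUARD". X.d describes FJS improvement over the first year and on to 2 years without naming arms.

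**Analysis method.** X.e defers all analyses to a Statistical Analysis Plan (SAP) to be completed before analysis, and Section XIII lists a SAP among the documents available on request. The plan itself names no primary test, gives the preoperative FJS no role, and does not say how the 13.4-point statement is judged. X.e rules out imputation and leaves a patient with missing data out of the analysis concerned.

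**FJS scoring.** VIII.F.e scores twelve items from 0 to 4 with 0 best, sums them, multiplies by 25, gives a total of 0 to 100, and equates a low score with high satisfaction. It then expects a higher score for ORIGIN. IV.B grades a mean of 12.9 as poor and 60.5 as good.

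**The concern.** The closing sentence of VI.B is the only place in the endpoint section that says how endpoints are evaluated, and it describes a different contrast from the one the trial was randomised and sized for. Most patients improve after a knee replacement, and V.A itself expects improvement with either device. A rule that asks only for significant improvement from baseline would be met in both arms whether or not the devices differ, so it could not support a statement about ORIGIN against VANGUARD.

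The sentence also cannot apply to endpoints that have no preoperative value, such as complications, revisions and surgeon satisfaction.

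Two gaps make this more than a stray line. X.e does not turn its superiority statement into a decision rule, and the possible readings differ widely in power. The FJS scoring text, followed literally, reverses the direction of the primary result. The study is not blinded (VII.C), so these choices are best fixed in the plan before data are seen.

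**Working it through.** **1. The plan's own sample size (X.a).** n = 2/ES² × (1.96 + 0.84)², with ES = 13.4/26.8 = 0.5. This gives 2/0.25 × 7.84 = 62.72, so 63 per group; adding 7 for loss gives 70. The figure reproduces as a two-sided between-arm comparison of means. Power at 63 per group is 80.1% by the normal formula and 79.5% by the t test.

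**2. The VI.B sentence read within one arm.** Inputs: n = 63; follow-up SD 26.8 (X.b); ORIGIN gain 60.5 − 12.9 = 47.6 (IV.B, a 1-year figure standing in for 2 years). Assumed, because the documents do not give them: baseline SD 10 to 26.8 and pre/post correlation r from 0 to 0.5.
- SD of change = √(26.8² + sb² − 2·r·26.8·sb), where sb is the baseline SD: 23.3 to 37.9.
- Smallest significant mean gain = t(0.975; 62) × SD/√63: 5.9 to 9.5 points.
- Gain of 47.6: t = 10.0 to 16.2.
- Gain of 34.2 (13.4 less): t = 7.2 to 11.7.

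An arm that improves as ORIGIN did and an arm that falls short of it by the full hypothesised difference both pass easily.

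**3. Three readings of the 13.4-point statement in X.e.** SE of the difference = 26.8 × √(2/63) = 4.78. With a true difference of 13.4:

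| Success requires | Probability of success |
|---|---|
| Lower 95% limit above 0 | about 80% |
| Estimate of at least 13.4 | 50% |
| Lower 95% limit above 13.4 | 2.5% |

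Only the first matches the 80% power used to reach 63. Under it, the smallest significant observed difference is about 9.5 points.

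**4. Adjusting for preoperative FJS.** Residual SD = 26.8 × √(1 − r²). At 63 per arm:

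| Analysis | r = 0.2 | r = 0.3 | r = 0.5 |
|---|---|---|---|
| Unadjusted | 79.5% | 79.5% | 79.5% |
| Adjusted, all baselines present | 81.1% | 83.1% | 89.5% |
| Adjusted, 3 per arm dropped for missing baseline | 79.2% | 81.3% | 88.0% |
| Adjusted, 6 per arm dropped | 77.1% | 79.2% | 86.3% |

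The correlations and the counts of 3 and 6 are illustrative. If missing baselines are filled with the overall mean, the residual variance is 26.8² × (1 − r²(1 − m/63)) for m missing per arm. Power is then 81.0% at r = 0.2 for either count, and 89.1% or 88.6% at r = 0.5.

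**5. FJS scoring (VIII.F.e).** Taken literally, the maximum is 12 × 4 × 25 = 1200, not 100, with low values best. With 100 − 25 × mean item score, all items at 0 give 100 and all at 4 give 0. That fits the 0-100 range, the expected higher ORIGIN score and the grading in IV.B.

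**The case against.** **The sentence may concern only secondary endpoints.** It closes the secondary subsection and echoes that list's 2-year wording, while the primary endpoint has its own time point. This is a fair reading, and it limits the finding. A reader might infer that the plan moves its primary endpoint to 2 years, or replaces the randomised comparison with a before-and-after test. The documents do not support that: it is one possible reading of an unqualified line, against consistent between-arm statements in the Synopsis, VI.B a), VI.C, VIII.F and X.a. The secondary-only reading does not remove the conflict, because VI.B b) and the Synopsis compare those scores between arms as well.

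**Some endpoints are already handled.** X.c reports adverse events and re-operations as proportions, and X.d covers surgeon satisfaction. So the sentence's inability to apply to such endpoints is a matter of wording.

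**The SAP may settle the analysis.** A reader might infer that the trial has no primary analysis. That cannot be shown, since a separate SAP is foreseen. What stands is that the plan states no test or success rule, and that a SAP following the between-arm design would have to contradict the VI.B sentence.

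**Lower limit above 0 allows success below 13.4.** True: an observed difference of about 9.5 would suffice, although X.b sets 13.4 as the minimal important difference. That is why the estimate should be reported against 13.4. The stricter readings do not fit the chosen sample size.

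**Adjustment is optional and brings a missing-baseline problem.** Correct. It is a precision gain, not a bias correction, and the core repair does not depend on it.

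**The 1200 maximum reflects an omitted averaging step.** Probably so, but the stated direction still contradicts the expected higher score.

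**Conclusion.** The concern holds in limited form. The last sentence of VI.B conflicts with the plan's between-arm comparisons whether it covers secondary endpoints only or all endpoints. Read within-arm, it would be met by both devices and could not support a device comparison. This rests on the assumed baseline SD and correlation and on a 1-year gain used in place of a 2-year one, but the margin is wide: 47.6 or 34.2 points against a threshold of 5.9 to 9.5. The documents give no VANGUARD change, 2-year values, baseline SD or correlation.

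The sections on the 1-year and 2-year visits show that a between-arm contrast is intended, so this is a text to correct and not evidence of a changed design. The sample size of 63 per group, 70 with losses, stands. The success rule should be stated because its possible readings span 80%, 50% and 2.5% power. The FJS formula and direction are wrong as written. It should be fixed, by wording alone.

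**What to change.** 1. **VI.B.** Replace the last sentence with: *Change from preoperative to 1 and 2 years is summarised by arm; conclusions about ORIGIN versus VANGUARD rest on between-arm comparisons, with FJS at 1 year as primary.* This keeps the before-and-after description that VI.A asks for. Align the FJS wording in X.d.
2. **X.e.** Add: *The primary analysis is the difference ORIGIN minus VANGUARD in 1-year FJS, adjusted for preoperative FJS, with a two-sided 95% confidence interval. Superiority is shown if the lower limit is above 0. The estimate is reported against the 13.4-point MCID. A missing preoperative FJS is replaced by the overall baseline mean, pooled over arms; this is the only exception to the missing-data rule of this section and applies to the baseline covariate only.*
3. **VIII.F.e.** State: *FJS = 100 − 25 × mean item score (items 0 to 4, 0 best); higher is better.* Remove the text that says the opposite.

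**Cost.** Protocol and SAP wording only; the sample size is unchanged. Preoperative FJS is already collected in both arms (VIII.F a and the schedule in XXI.B). The downside is one stated exception to the missing-data rule, and the precision gain depends on a correlation the documents do not give.

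Whether the satisfaction questionnaire is primary or secondary is a separate point and is not settled here.
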